8.2 Background Characteristics

8.2.1 Subject Disposition

For the Treatment Period in Parts 1 and 2, subject disposition will be summarized as described below.

The number of subjects in the following categories will be summarized by treatment group and overall for each part, as applicable:

- All Subjects Set
- Randomized
- Full Analysis Set (FAS)
- Safety Set (For Part 2, this is the Safety Set for the Treatment Period)

The number and percentage (based on FAS) of subjects in each of the following disposition categories will be summarized by treatment group and overall:

- Completed study drug treatment
- Prematurely discontinued treatment and the reason for discontinuation (i.e. discontinued all study drugs)
- Completed study (i.e., completed Safety Follow-up Visit or completed all study drug and re-entered Study 661-110 without Safety Follow-up per protocol)
- Prematurely discontinued the study and the reason for discontinuation

For the Run-in Period in Part 2, a separate disposition table will be provided with the following categories:

- Safety Set for the Run-in Period
- Enrolled but not dosed in the Run-in Period
- Completed treatment in the Run-in Period (i.e., completed randomization)
- Prematurely discontinued treatment during the Run-in Period and the reason for treatment discontinuation (i.e., discontinued all study drugs in the Run-in Period)
- Prematurely discontinued the study during the Run-in Period and the reason for study discontinuation

A listing will be provided by part, for subjects who discontinued treatment (including the Run-in Period in Part 2) or who discontinued study with reasons for discontinuation. A randomization listing of subjects will also be provided, by part.

8.2.2 Demographics and Baseline Characteristics

Demographics, medical history and baseline characteristics will be summarized based on the FAS, and presented by treatment group and overall, for each part, as applicable.

Demographic data will include the following:

- Age at baseline (in years)
- Sex (female and male)
- Ethnicity (Hispanic or Latino, not Hispanic or Latino, and not collected per local regulations)
- Race (White, Black or African American, Asian, American Indian or Alaska Native, Native Hawaiian or Other Pacific Islander, and Other)

Baseline characteristics will include the following:

- Weight (kg)
- Height (cm)
- BMI (kg/m^2)

Disease characteristics will include the following:

- ppFEV₁ at baseline ($<40, \ge 40$ to $<70, \ge 70$ to $\le 90, >90$)
- ppFEV₁ at baseline (continuous)
- Sweat Chloride at baseline (continuous)
- FEV₁ (L) at baseline (continuous)
- CFQ-R Respiratory Symptoms domain at baseline (continuous)
- Prior use of dornase alfa before first dose of study drug (Yes, No)
- Prior use of inhaled antibiotic before first dose of study drug (Yes, No)
- Prior use of any bronchodilator before first dose of study drug (Yes, No)
- Prior use of any inhaled bronchodilator before first dose of study drug (Yes, No)
- Prior use of any inhaled hypertonic saline before first dose of study drug (Yes, No)
- Prior use of any inhaled corticosteroids before first dose of study drug (Yes, No)
- Infection with Pseudomonas aeruginosa at baseline (Positive, Negative)

Medical history will be summarized by MedDRA system organ class (SOC) and preferred term (PT) based for the FAS. In addition, the number of subjects reported to have had positive cultures for respiratory pathogens in 2 years prior to screening will be summarized for the FAS.

8.2.3 Prior and Concomitant Medications

Medications used in this study will be coded by using the World Health Organization Drug Dictionary Enhanced (WHO-DDE) and categorized as the following:

For Part 1:

Prior medication: any medication that started before the first dose date of study drug, regardless of when the medication ended.

Concomitant medication: medication continued or newly received on or after the first dose date of study drug through the end of the TE period.

Post-treatment medication: medication continued or newly received after the TE period.

For Part 2:

Prior medication: any medication that started before the first dose date of study drug in the Run-in Period, regardless of when the medication ended.

Concomitant medication during the Run-in Period: medication continued or newly received on or after the first dose date of study drug during the Run-in Period through the end of TE period for the Run-in Period.

Concomitant medication during the Treatment Period: medication continued or newly received on or after the first dose date of study drug during the Treatment Period through the end of TE period for the Treatment Period.

Post-treatment medication: medication continued or newly received after the TE period.

A given medication may be classified as follows: prior, concomitant, post-treatment, both prior and concomitant, both concomitant and post-treatment, or prior, concomitant, and post-treatment. Concomitant for Part 2 can be concomitant during the Run-in Period, concomitant during the Treatment Period, or both.

If a medication has a completely missing or partially missing start/stop date and it cannot be determined whether it was taken before the first dose date of study drug, concomitantly, or after the TE period, it will be classified as prior, concomitant, and post-treatment.

Prior medications and concomitant medications will be summarized descriptively using frequency tables by preferred name.

Summaries of medications will be based on the FAS, and presented by treatment group and overall for each part.

Post-treatment medications will be listed only.

Details for imputing missing or partial start and/or stop dates of medication are described in Appendix C.

8.2.4 Study Drug Exposure

Study drug exposure (in days) will be calculated as: last dose date of study drug – first dose date of study drug + 1 day, regardless of study drug interruption, and will be summarized descriptively. Study drug exposure will be summarized for the overall study drug period,

which includes the Run-in Period, Treatment Period and Washout Period for Part 2, and the Treatment Period for Part 1. Further, study drug exposure for the combined Treatment Period and Washout Period in Part 2 will also be summarized descriptively.

Study drug exposure (in weeks) will be summarized descriptively by the number of subjects (n), mean, SD, SE, median, min, and max. It will also be summarized in categories: ≤ 2 weeks, $\geq 2 - \leq 4$ weeks, $\geq 4 - \leq 6$ weeks and ≥ 6 weeks, using counts and percentages. Additionally, the total study drug exposure, defined as the sum total of the study drug exposure across all subjects (in patient-weeks), will be provided.

Exposure summaries will be based on the Safety Set, and presented by treatment group and overall, for each part. For Part 2, exposure summaries will be based on the Safety Set for the Treatment Period.

8.2.5 Study Drug Compliance

Percentage of tablets taken will be calculated as: $100 \times [(\text{total number of tablets dispensed}) - (\text{total number of tablets returned})]/(total number of tablets planned to be taken per day × duration of study drug exposure in days). The maximum percentage of tablets taken will be 100%.$

Study drug compliance will be calculated as: $100 \times [1 - (\text{total number of days of study drug interruption}) / (duration of study drug exposure in days)]. A study drug interruption on a given day will be determined by an interruption of all drugs on that day.$

Percentage of tablets taken and study drug compliance will be summarized descriptively by the number of subjects (n), mean, SD, SE, median, min, and max. It will also be summarized in categories: <80% and $\ge80\%$ using frequency tables.

For all parts, study drug compliance will be summarized for the Treatment Period only. Similarly, for all parts, percentage of tablets taken will be summarized for the Treatment Period only.

Percentage of tablets taken and study drug compliance summaries will be based on the FAS, and presented by treatment group and overall, for each part.

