^w Blood samples will be collected for PK analysis of VX-152, VX-661, M1-661, IVA, and M1-IVA. On Day 1, samples will be collected before dosing (0 hours) and at 1, 2, 4, and 6 hours after dosing (relative to the morning dose). On Day 8, a predose sample will be collected before the morning dose of study drug (0 hours). On Day 15, samples will be collected before dosing (0 hours) and at 1, 2, 4, 6, and 8 hours after dosing. At the ETT Visits, a single blood sample for PK analysis will be collected.

^x The last dose of study drug will be the morning dose on Day 15.

^y Refer to [Section 9.4](#) for details.

Table 3-2 Study VX16-152-102: Schedule of Assessments for Part 2, Cohort 2A

Event/Assessment ^a	Screening	Run-in Period		Treatment Period ^b					Washout Period	ETT Visit ^c	Safety Follow-up 28 (± 7) Days After Last Dose ^d
	Days -56 to -29 ^e	Day -28 (± 1 day)	Day -14 ^f (± 1 day)	Day 1	Days 3 and 5 ^g (or Days 4/6 or Days 3/6) ^h	Day 8 (± 1 day)	Day 11 ^g (± 1 day)	Day 15 (± 1 day)	Day 29 (± 3 days)		
Informed consent	X										
Randomization ⁱ				X							
Demographics	X										
Medical history	X										
Ophthalmological history	X										
CFQ-R ^{j,k}				X		X		X	X	X ^l	X
Weight ^m	X	X		X		X		X	X	X	X

- ^a Assessments will be performed in the order presented, unless noted otherwise. All assessments will be performed before dosing, unless noted otherwise. Assessments that are collected before and after dosing will only be collected once if study drug is not administered on the day of the visit (i.e., premature discontinuation of study drug treatment).
- ^b To be eligible to continue into the Treatment Period, subjects must have stable CF disease and have remained on stable CF medication regimen during the 28 days before the Day 1 Visit AND must not have had an acute non-CF illness within 14 days before the Day 1 Visit. See [Section 8.1.3](#).
- ^c If the subject prematurely discontinues study treatment, an ETT Visit should be scheduled as soon as possible after the decision to terminate study drug treatment. Subjects who prematurely discontinue treatment will also be required to complete the Safety Follow-up Visit. If the ETT Visit occurs 3 weeks or later following the last dose of study drug, then the ETT Visit will replace the Safety Follow-up Visit, and a separate Safety Follow-up Visit will not be required.
- ^d Subjects who meet criteria specified in [Section 8.1.5](#) will not have a Safety Follow-up Visit.

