- f) E17: Pregnant or nursing females: Females of childbearing potential must have a negative pregnancy test at screening and Day 1.

Important protocol deviations during the Treatment Period

- 1. Compliance < 80% based on percentage of tablets taken
- 2. Use of prohibited medications
- 3. Actual treatment received is different from the randomized treatment

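### The tablet-count denominator in SAP 8.2.5 includes a last-day evening dose that is not scheduled, so a fully adherent Part 1 completer reads 96.7%

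*SAP*

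**What the plan says.** The points that matter are these.

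- **End of dosing, Part 1.** Protocol Table 3-1 (footnote x), repeated in SAP Appendix A: "The last dose of study drug will be the morning dose on Day 15".
- **End of dosing, Part 2.** Protocol Tables 3-2 and 3-3 stop VX-152 or placebo with the morning dose on Day 15 (Cohort 2A) or Day 29 (Cohort 2B). VX-661/IVA continues to the morning of Day 29 or Day 43.
- **Exposure.** SAP 8.2.4 uses "last dose date of study drug – first dose date of study drug + 1 day, regardless of study drug interruption".
- **Percentage of tablets taken.** In SAP 8.2.5 the numerator is tablets dispensed minus tablets returned. The denominator is "total number of tablets planned to be taken per day", multiplied by the exposure days. The result has an upper limit: "The maximum percentage of tablets taken will be 100" percent. Protocol 12.3.2.4 gives the same ratio. Neither document adjusts for a single dose on the last day.
- **Study drug compliance.** SAP 8.2.5 defines this separately, from interruption days: "A study drug interruption on a given day will be determined by an interruption of all drugs on that day".
- **Deviation rule.** SAP Appendix D flags "Compliance < 80% based on percentage of tablets taken".

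**The concern.** A compliance measure should read 100% for a subject who takes every scheduled tablet. This one cannot do so for a Part 1 completer, because the inclusive day count is multiplied by a full day's tablets although the last day has only a morning dose. The cap limits high readings and does nothing for a low one.

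The shortfall also differs between Part 1 and the two Part 2 cohorts, so their tablet figures are not on the same scale. The affected measure is the one that Appendix D uses to flag possible important deviations. At stake are the accuracy of a descriptive summary and the meaning of the 80% line.

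**Working it through.** The documents state no compliance figure for a fully adherent subject, so there is nothing of theirs to reproduce. The SAP formulas are applied directly.

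**Inputs.** Let n be the number of 100-mg VX-152 (or placebo) tablets per dose: 1, 2 or 3 for 100, 200 or 300 mg every 12 hours. Protocol Table 10-1 gives one VX-661/IVA tablet in the morning and one IVA tablet in the evening. That makes n+1 tablets in the morning, n+1 in the evening and 2n+2 per day.

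**Part 1.** Exposure = 15 − 1 + 1 = 15 days.

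- Scheduled tablets: 14(2n+2) + (n+1)
- SAP denominator: 15(2n+2)
- Ratio: 14.5/15 = 96.7% for every n

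| n | Scheduled | SAP denominator | Reading at full adherence |
|---|---|---|---|
| 1 | 58 | 60 | 96.7% |
| 2 | 87 | 90 | 96.7% |
| 3 | 116 | 120 | 96.7% |

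The ±1 day visit window changes this little. A last dose on Day 14 gives 13.5/14 = 96.4%, and on Day 16 it gives 15.5/16 = 96.9%.

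**Sensitivity to tablet counts.** The IVA row of Table 10-1 also lists 150 mg every 12 hours. If that meant one more IVA tablet each morning, the readings would be 73/75 = 97.3%, 102/105 = 97.1% and 131/135 = 97.0%.

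**The other measure.** With no interruption, study drug compliance = 100 × (1 − 0/15) = 100%.

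**Part 2, all study drugs counted over the VX-152 or placebo dosing days.** The IVA tablet on the evening of the last VX-152 or placebo day is still scheduled, so only the n evening VX-152 or placebo tablets are over-counted.

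- Cohort 2A (n = 2, 15 days): denominator 15 × 6 = 90; scheduled 90 − 2 = 88; 88/90 = 97.8%
- Cohort 2B (n = 3, 29 days): denominator 29 × 8 = 232; scheduled 232 − 3 = 229; 229/232 = 98.7%

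**Effect on the 80% flag, Part 1.** There are 29 scheduled doses and the denominator is worth 30. A reading of 80% corresponds to 0.80 × 30/29 = 82.8% of scheduled doses.

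- 24 whole doses: 24/30 = 80.0% exactly, not flagged; true value 24/29 = 82.8%
- 23 whole doses: 23/30 = 76.7%, flagged; true value 23/29 = 79.3%, also below 80%

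No whole-dose count changes category. Only totals that include partly taken doses do: 47 tablets for n = 1 (47/60 = 78.3% against 47/58 = 81.0%), 70 or 71 for n = 2, and 93 to 95 for n = 3.

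**Exposure categories, a separate matter.** Taking a week as 7 days, 15 days is 2.14 weeks, just above the 2-week cut. A last dose on Day 14 gives exactly 2.00 weeks and on Day 16 gives 2.29. Counting Day 15 as half a day still gives 14.5/7 = 2.07 weeks.

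**The case against.** The best case against the point is that it hardly matters, and much of that stands. The summaries are descriptive. A flagged subject is only a potential important deviation, a blinded team decides whether it counts, and the result is a listing (SAP 8.2.6). No analysis set in SAP Section 7 excludes subjects for compliance. Subjects take the same number of tablets each day to keep the blind (Protocol 10.2), so within a cohort the shortfall is the same in both arms.

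Several stronger readings are tempting, but the documents do not support them.

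- *Every tablet figure is too low.* A subject who stops after an evening dose has a correct denominator. Tablets lost or not returned count as taken, which pushes the figure up. The net direction for a given subject is not known.
- *Compliance in general reads 96.7%.* Only the percentage of tablets taken does. The measure that the SAP names study drug compliance reads 100%.
- *The half-dosed last day puts 2-week completers in the next exposure category.* It does not, since 14.5 days is still above 2 weeks. The cause is the inclusive day count set against a cut at 14 days.
- *In Part 2 every subject would be flagged.* SAP 8.2.4 defines Part 2 durations only for the whole dosing period and for Treatment and Washout combined: 57 and 29 days in Cohort 2A. Dividing 15 days' tablets by those spans would give about 26% or 52%. But SAP 8.2.5 limits both measures to the Treatment Period, and the natural reading applies that limit to numerator and denominator alike. What is missing is a statement of the duration.

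**Conclusion.** The point holds as a small arithmetic error in a stated formula. For a Part 1 completer the percentage of tablets taken is understated by 3.3 percentage points at full adherence (96.7% instead of 100%), or by 2.7 to 3.0 points if the second IVA entry in Table 10-1 applies. In Part 2 the understatement is 2.2 points in Cohort 2A and 1.3 points in Cohort 2B, provided that the duration is taken as the VX-152 or placebo dosing days and the last evening's IVA tablet is counted.

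The result assumes a first dose in the morning, a last dose as scheduled, complete tablet returns and the tablet counts inferred from Table 10-1. The effect on the deviation flag is confined to a few tablet totals. No efficacy or safety conclusion changes. It is worth correcting because the correction is cheap, but it is not a serious flaw.

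**What to change.** 1. In SAP 8.2.5, replace the denominator with the number of tablets scheduled from the first to the last dose in the Treatment Period, summed by component. For Part 1, count no evening tablets on the last day. For Part 2, count no evening VX-152 or placebo tablets on their last day, and say explicitly whether that evening's IVA tablet is counted. Dropping all last-day evening tablets in both parts would be wrong, because in Part 2 that IVA tablet is scheduled. With this denominator a fully adherent subject reads 100%.
2. State that for Part 2 the duration in both compliance formulas runs from first to last VX-152 or placebo dose.
3. Reconcile the two IVA entries in Protocol Table 10-1, so that the tablets planned per day are unambiguous.
4. Optionally, and separately, move the exposure-category cuts in SAP 8.2.4 away from the planned durations, so that the ±1 day visit window does not split 2-week completers.

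The SAP items cost wording and a programming change, and item 3 is a clarification of one protocol table. There are no new data to collect.

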8.2.6 Important Protocol Deviations

An important protocol deviation (IPD) is a deviation that may significantly affect the completeness, accuracy, or reliability of the study data or that may significantly affect a subject's rights, safety, or well-being. IPD rules will be developed and finalized before database lock.

The protocol deviations that should be considered as potential IPDs include, but are not limited to:

- Subject was enrolled in the study despite the violation of inclusion/exclusion criteria
- Subject was less than 80% compliant with study drug
- Subject received prohibited concomitant medications
- Subject received the wrong treatment or incorrect doses

• Subject remained in the study despite meeting withdrawal criteria

Occurrence of any of these events should be considered as potential IPDs, but a blinded team should categorize them as IPDs only if they have the potential to significantly affect the completeness, accuracy, or reliability of the study data or that may significantly affect a subject's rights, safety, or well-being.

IPDs will be provided in an individual subject data listing. Details of the IPD rules are provided in Appendix D.

8.3 Efficacy Analysis

All efficacy analyses described in this section will be based on the FAS, unless otherwise specified. The placebo groups will be pooled across all cohorts in Part 1. The TEZ/IVA groups of varying durations during the Treatment Period (2 weeks and 4 weeks) will be kept separate in Part 2, unless specified otherwise. The analysis will include all available measurements through the last scheduled on-treatment visit including measurements after treatment discontinuation, per the visit windowing rules described in Appendix B. The post-dose measurements on the same day will not be used for any model-based analyses.

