10 STUDY DRUG ADMINISTRATION AND MANAGEMENT

Study drug refers to VX-152, VX-661/IVA, IVA, and their matching placebos.

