For Part 2, the TE period will be defined separately for the Run-In Period, and the Treatment Period:

- The TE period for the Run-in Period will include the time from the first dose of study drug in the Run-in Period to: (1) the last day prior to the first dose of study drug in the Treatment Period for subjects who complete the Run-in Period and continue to the Treatment Period, or (2) the SFU Visit for subjects who did not continue to the Treatment Period and have an SFU Visit, or (3) 28 days after the last dose of study drug in the Run-in Period for subjects who do not have an SFU Visit (e.g., subjects who do not meet the criteria to enter the Treatment Period and re-enter Study 661-110). Only data collected up to the end of study for a subject will be included in analysis.
- The TE period for the Treatment Period will include the first dose of study drug in the Treatment Period to: (1) the SFU Visit, or (2) 28 days after the last dose of study drug for subjects who do not have an SFU Visit (e.g. subjects whose Early Treatment Termination (ETT) Visit occurs 3 weeks or later following the last dose of study drug and the ETT visit replaces the SFU visit, or who leave the study early and re-enter Study 661-110). Only data collected up to the end of study for a subject will be included in analysis.

Unscheduled visits: Unscheduled visit measurements will be included in analysis as follows:

- In scheduled visit windows per specified visit windowing rules.
- In the derivation of baseline/last on-treatment measurements.
- In the derivation of maximum/minimum on-treatment values and maximum/minimum change from baseline values for safety analyses.
- In individual subject data listings as appropriate.

Visit windowing rules: The analysis visit windows for protocol-defined visits are provided in Appendix B.

Spirometry ($ppFEV_1$) will be used for both efficacy and safety purposes. For efficacy analysis, the assessments will follow the visit windowing rules for efficacy. For safety analysis, the assessments at 5 hours post-dose on nominal days 1 and 15 will be used.

Incomplete/missing data will not be imputed, unless specified otherwise.

Outliers: No formal statistical analyses will be performed to detect or remedy the presence of statistical outliers, unless specified otherwise.

Multiplicity: There will be no multiplicity adjustment for performing multiple hypothesis tests, unless specified otherwise.

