8.3.1.1 Primary Analysis of the Primary Efficacy Variable

The null hypothesis to be tested is that the mean absolute change from baseline in percent predicted FEV_1 (ppFEV₁) is not greater than zero for VX-152 in triple combination (TC) with VX-661/IVA at Day 15 in Part 1 and Part 2 Cohort 2A and through Day 29 in Part 2 Cohort 2B.

Part 1:

The primary analysis will be performed using a mixed-effects model for repeated measures (MMRM) with change from baseline in ppFEV₁ as the dependent variable. This MMRM analysis will include all treatment groups within Part 1, including placebo, VX-152 100mg, VX-152 200mg and VX-152 300mg. The model will include treatment group, visit, and treatment-by-visit interaction as fixed effects, with the continuous baseline ppFEV1 as a covariate, and will include all data from each treatment group and visit up to Day 15. The model will be estimated using restricted maximum likelihood. Denominator degrees of freedom for the F test for fixed effects will be estimated using the Kenward-Roger approximation. A compound symmetry covariance structure will be used to model the within-subject errors. Conditional on the observed data and covariates, missing ppFEV₁ data due to treatment or study discontinuation will be assumed to be missing at random; consequently, no imputation of missing data will be performed.

The adjusted means and 95% confidence intervals (CI) of the treatment effect for each triple combination at Day 15, with a 1-sided P value, will be estimated within MMRM using PROC MIXED in SAS, for all within-treatment and between-treatment comparisons. Contrasts based on the fixed effects in the model, defined at the baseline covariate mean for the combined treatment groups using unique subjects in the FAS who have at least one postbaseline measurement through Day 15, will be used to estimate the treatment effect at Day 15, with the corresponding 1-sided P value for the 1-sided hypothesis test.

Further, the adjusted mean and the 2-sided 95% CI of the treatment difference for withingroup and between-group comparisons at each post-baseline visit up to Day 15 will be provided.

In addition, descriptive analyses of the change from baseline will be performed for all treatment groups by post-baseline visit.

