8.3.2 Analysis of Secondary Efficacy Variables

The secondary efficacy variables include:

- Relative change in ppFEV₁ from baseline at Day 15 (Part 1 and Part 2 Cohort 2A) and through Day 29 (Part 2 Cohort 2B)
- Absolute change in the CFQ-R respiratory domain score from baseline at Day 15 (Part 1 and Part 2 Cohort 2A) and at Day 29 (Part 2 Cohort 2B)

8.3.2.1 Relative change in ppFEV1 from baseline at Day 15 (Part 1 and Part 2 Cohort 2A) and through Day 29 (Part 2 Cohort 2B)

The relative change in $ppFEV_1$ from baseline is defined in Section 8.1. Analysis of this variable will be based on an MMRM model, similar to the primary analysis of the primary efficacy variable. The presentation of results will also be similar.

8.3.2.2 Absolute change in the CFQ-R respiratory domain score from baseline at Day 15 (Part 1 and Part 2 Cohort 2A) and at Day 29 (Part 2 Cohort 2B)

The absolute change in the CFQ-R respiratory domain score from baseline at Day 15 (Part 1 and Part 2 Cohort 2A) and at Day 29 (Part 2 Cohort 2B) will use the 'Adolescents and Adults' Version for ages 14 and above at baseline, and will be based on the *CFQ-R scaled scores*,

For Part 1, the analysis of this variable will be based on an ANCOVA model with treatment as a fixed effect. For Part 2, the analysis of this variable will be based on an MMRM model, similar to the analysis of the primary efficacy variable. The continuous baseline CFQ-R respiratory domain score will be used as a covariate in Parts 1 and 2. The presentation of results will also be similar.

· -	

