8.4 Pharmacodynamic Analysis

The sweat chloride measurement for a given visit will be calculated as the mean of the nonmissing sweat chloride measurements obtained on the left and right arms at that visit. If one of the two arm measurements at a time point is missing, the other will be used as the mean. A volume $\geq 15 \ \mu$ L is required for an accurate determination of sweat chloride. Any results reported as having volume <15 μ L will be considered missing. Any sweat chloride values reported as <10 mmol/L or >160 mmol/L will be considered missing.

The analysis of the pharmacodynamic (PD) effect of VX-152 in TC with VX-661/IVA (all parts) on sweat chloride concentrations will be described in this section.

8.4.1.1 Primary Analysis of the Dose Response trend of absolute change in sweat chloride from baseline at Day 15 in Part 1

The null hypothesis to be tested is that the dose response of the mean absolute change from baseline at Day 15 for sweat chloride is not decreasing between placebo and the TC dose groups. The test will be performed using the MCP procedure with the pre-specified contrasts provided in Section 6.2.2.1, within a linear MMRM framework using PROC GLIMMIX in SAS. The model will include treatment group, visit, and treatment-by-visit interaction as fixed effects, with continuous baseline sweat chloride as a covariate. The dose response test will be based on the 1-sided maximum *t*-statistic of the individual *t*-statistics for the multiple pre-specified contrasts at alpha = 5%, based on the treatment group means at Day 15, using a compound symmetry covariance structure for the within-subject errors

The presentation of results for the treatment effect at Day 15, and the treatment effect by visit will be similar to the primary analysis of the primary efficacy variable. The corresponding P value for the decreasing dose response trend will be provided. In addition, descriptive analyses of the change from baseline will be performed for all treatment groups at each postbaseline visit. A waterfall plot showing the subject-level absolute change from baseline in sweat chloride at Day 15 will be presented, by treatment group.

[figure not shown]
8.4.1.2 Absolute change in sweat chloride from baseline at Day 15 (Part 2 Cohort 2A) and through Day 29 (Part 2 Cohort 2B)

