	Day 15	15	(12, 22]
	Day 29	29	(22, 36]
	Day 43	43	(36, 57]
	Safety Follow-up	71	Use nominal
			visit

- i. If there are no measurements at the scheduled visit, then the measurement closest to the target day will be used; or
- ii. If there are multiple measurements with the same distance to the target day, the latest measurement will be used.
- b. For safety parameters: if there are multiple measurements within a visit window,
 - i. The measurement closest to the target day will be used; or
 - ii. If there are multiple measurements within the same distance from the target day, the latest measurement will be used.
 - iii. For tables of the extreme lab measurement based on ULN or LLN, convert the lab measurements into times of ULN or LLN first, and then select the extreme measurement.

Assessment	Visit ^a	Target Study Day ^b	Analysis Visit Window (in study days)
Derived Variables			-
1. Age (in years) at first dose date			
Obtain age at screening (in days) in yy mm for and add 0.5 month to convert to days.	rmat (e.g., 24 years, 6 months)	from screening vi	tal signs page,
Obtain screening date from Date of Visit (DO	V) page.		
Then age (in years) at first dose date = integer screening (in days)]/365.25}.	part of {[(first dose date-screen	ning date) in days	+ age at
Correspondingly, age (in months) at first dose days + age at screening (in days)]/365.25}.	date = integer part of 12*{[(fir	st dose date-scree	ning date) in
2. Age (in years) at post-baseline visit (for u	se in calculation of percent pre	dicted spirometry	variables)
Age (in years) at post-baseline visit = integer j at screening (in days)]/365.25}	part of {[(post-baseline visit dat	te – screening date	e) in days + age
3. Missing First Dose Date or Last Dose Dat	te		
If the first dose date is missing, use Day 1 visi	t date.		
If the last dose date is missing at final analysis and last study drug administration date from E lost to follow up without ETT, impute the last	X SDTM domain (excluding P	K dosing dates).	
4. Missing Date for Drug Interruption			

If the dates for drug interruption are completely missing or partially missing and cannot determine which period the interruption occurred, then assume the interruption occurred during the treatment period for 1 day.

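### Does the Part 1 Day 15 efficacy window, which runs to Day 29, let off-drug values distort the Day 15 result enough to need changing?

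*SAP*

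**What the plan says.** SAP 8.3 includes "all available measurements through the last scheduled on-treatment visit including measurements after treatment discontinuation, per the visit windowing rules described in Appendix B". For Part 1, Appendix B sets the Day 15 window at (12, 29] for spirometry and sweat chloride and (1, 29] for CFQ-R. Safety Follow-up is assigned by nominal visit only. SAP 8.1 places unscheduled values "In scheduled visit windows per specified visit windowing rules". The selection notes under the Appendix B window table add: "If there are no measurements at the scheduled visit, then the measurement closest to the target day will be used".

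Three Part 1 analyses use the Day 15 value:

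- The ppFEV1 model (SAP 8.3.1.1) "will include all data from each treatment group and visit up to Day 15".
- The sweat chloride dose-response test (SAP 8.4.1.1) is "based on the treatment group means at Day 15".
- For CFQ-R (SAP 8.3.2.2), "For Part 1, the analysis of this variable will be based on an ANCOVA model with treatment as a fixed effect".

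The protocol's Table 3-1 schedules the visit at Day 15 ± 1 day and states: "The last dose of study drug will be the morning dose on Day 15". Protocol Section 10 makes clear that this covers the whole regimen: "Study drug refers to VX-152, VX-661/IVA, IVA, and their matching placebos".

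**The concern.** The analysis window is much wider than the visit window, and nearly all the extra width lies after dosing has ended. A spirometry or sweat chloride value from as late as Day 29, 14 days after the planned last dose, can carry the Day 15 label. The protocol itself treats about two weeks after VX-152 as an off-treatment measurement in Part 2 (Section 8.1.4). The SAP's references to the last scheduled on-treatment visit and to visits up to Day 15 suggest an earlier stop, but SAP 8.3 then defers to Appendix B.

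With 9 subjects per triple-combination group, one value is 11% of the group. If the effect had worn off, the Day 15 means that carry the Part 1 efficacy and dose-response results would be pulled towards zero.

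**Working it through.** **1. Where Day 29 comes from.** The target days in Appendix B are 15 for Day 15 and 43 for Part 1 Safety Follow-up: (15 + 43)/2 = 29. The same midpoint rule gives the other late limits: (15 + 29)/2 = 22, (29 + 43)/2 = 36, (29 + 57)/2 = 43 and (43 + 71)/2 = 57. Part 1 is wider than Cohort 2A only because it has no visit between Days 15 and 43.

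**2. How much of the window is late.** (12, 29] holds Days 13 to 29, which is 17 days. Days 17 to 29, or 13 of them, lie beyond Day 15 + 1. This counts calendar days, not values.

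**3. What has to happen for a late value to be used.** The scheduled Day 15 value must be missing. Then one of two things must occur:

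- An early-termination visit, due as soon as possible (protocol 8.1.6), slips past Day 16.
- An unscheduled test happens to fall on Days 17 to 29.

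A completer's Safety Follow-up, 28 ± 7 days after a Day 15 last dose, falls on Days 36 to 50 and is nominal in any case. An early-termination visit that replaces Safety Follow-up (3 weeks or later after last dose) can fall in the window only if the last dose was by Day 8, since 8 + 21 = 29.

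**4. Reproducing the plan's power.** One-sided one-sample t-test at 5%, SD 13 mmol/L, n = 9 (SAP Table 6-4): 67.8% at -10 and 93.4% at -15, against 68% and 93% stated. For ppFEV1, SD 8, 5 points (Table 6-5): 52.8% against 53%.

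**5. One off-drug value in a group of 9.** If it keeps a fraction r of the effect, the group mean is d × [1 - (1 - r)/9]. For d = -10 this is -8.9, -9.4 and -9.7 at r = 0, 0.5 and 0.75. Power with the value kept (simulated) or missing:

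| Analysis | Kept, r = 0 | Kept, r = 0.5 | Kept, r = 0.75 | Missing |
|---|---|---|---|---|
| Sweat chloride -10, one-sample t | 56.9% | 63.1% | 65.4% | 62.4% |
| Sweat chloride -15, one-sample t | 84.9% | 90.3% | 92.0% | 90.0% |
| ppFEV1 5 points, one-sample t | 44.0% | 48.8% | not run | 48.0% |
| Sweat chloride -10, MMRM | 63.2-63.3% | 68.0% | 70.2-70.3% | 68.2-70.0% |
| Dose-response max-t, Table 6-3 linear profile, value in Cohort 1C | 89.4% | 92.1% | not run | 93.4% |

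The MMRM rows use four groups of 9, Days 8 and 15, compound symmetry, an assumed within-subject correlation of 0.3 to 0.7, and 31 degrees of freedom in place of Kenward-Roger. With all values on drug, the max-t simulation gives 94.0%, against 94% stated.

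In the one-sample test, excluding the value gains 62.4 - 56.9 = 5.5 points at r = 0 and loses 65.4 - 62.4 = 3.0 points at r = 0.75. In the MMRM it gains 4.9 to 6.8 points at r = 0, 0.2 to 2.0 at r = 0.5, and loses 0.2 to 2.1 at r = 0.75. The max-t test gains 4.0 and 1.3 points at r = 0 and 0.5. All of these assume the absent subject would have responded like the rest.

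**6. What exclusion costs.** Suppose the absent subject would have responded half as well. The true mean is (8 × -10 + -5)/9 = -9.44. Treating the value as missing at random gives about -10, an overstatement of up to 0.56 mmol/L before any correction from Day 8 data.

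For CFQ-R, an early-termination form is completed only two weeks or more after the last visit. It can come no earlier than Day 3 + 14 = Day 17, or Day 7 + 14 = Day 21 after a Day 8 (± 1) visit. A cap at Day 16 would remove these forms from the main analysis and drop those subjects from the ANCOVA.

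**7. Whether a cap would isolate on-drug values.** A subject who stops on Day 2 but attends the Day 15 visit is 13 days off drug and stays in. A completer tested on Day 18 is 3 days off drug and goes out. The cap sorts by visit label, not by exposure.

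**The case for a change.** The strongest opposing point concerns completers. Including data after discontinuation is a reasonable treatment-policy choice for early stoppers, but it does not explain calling a Day 25 value Day 15 when every subject's planned dosing has ended. Two programmers could also differ on whether the last scheduled on-treatment visit in SAP 8.3 means a calendar cut or the Appendix B window. The SAP does not say how an early-termination visit that replaces Safety Follow-up is windowed. And if the effect vanished completely, excluding the value would help in every analysis tabulated.

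The ambiguity stands, and so does the conditional description of what could happen. The inference that the window must be shortened does not. No document shows that the full effect is lost within two weeks of stopping in Part 1; the protocol places Part 1's off-treatment measurement at Safety Follow-up (Section 8.2.1). The opening line of the efficacy selection rule in Appendix B is also lost from the text available here, so a limit stated there cannot be ruled out, and the loss cannot be counted against the plan.

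**Conclusion.** No change is needed. The wide window is the ordinary result of a midpoint rule, and SAP 8.3 openly chooses to use data after discontinuation. The route by which a late value reaches the Day 15 analysis is narrow, so few subjects should be affected.

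For one such subject in a group of 9, keeping the value moves a -10 mmol/L mean by at most 10/9 = 1.1 mmol/L, towards no effect. Removing it changes power by roughly +7 to -3 points at -10, depending on how much effect remains and which test is used. It also adds a possible overstatement of about 0.6 mmol/L and loses CFQ-R forms. That is a fair trade-off, not an error, on secondary endpoints of a study whose primary objective is a descriptive safety evaluation.

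These sizes rest on assumed retention, one affected subject and assumed correlations; the documents supply none of these. The remaining ambiguities are ones the analysts can settle, and record in the programming specification, before unblinding.
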